1.0 Objectives / Specific Aims

In individuals post-stroke and other CNS disorders, one of the most common and disabling problems is spasticity (12, 35, 36, 40), which is defined as a velocity-dependent reaction to passive range of motion, and often is demonstrated concurrently with increased resting muscle tone (12, 35-39). In chronic situations, spasticity can lead to secondary changes in spinal and supraspinal pathways (1, 2) and when coupled with muscular weakness these reflex changes can ultimately limit joint motion and impair motor control. Furthermore, when untreated or treated inadequately, spasticity can contribute to increased pain and joint contractures, thereby negatively impacting quality of life (12, 35, 36, 40). Currently, the most common approaches to treat spasticity are pharmacological treatments (12, 3-13) and standard physical therapy (including stretches, massages, and transcutaneous electrical stimulation). Recently, as a potential adjunct to these approaches, an increasing number of physical therapists worldwide have started administering trigger point deep dry needling (DDN) to treat spasticity and associated pain in people with CNS injuries(14-22). Locally, DDN at myofascial trigger points (MTrP) disrupts dysfunctional motor end plates and increases the local blood flow and oxygenation (68, 69) while stimulating nociceptors (60). Conceivably, excitation of nociceptors would influence the excitability of multiple spinal and supraspinal pathways (for example A- β and A- δ (group II/III) sensory afferents (60-64)). To date, the effects of DDN on spinal somatosensory processing are not well understood. To define the clinical utility of DDN in treating spasticity and related sensorimotor disorders, it is essential to understand its neurophysiological impact on CNS pathways. The understanding of the neurophysiological effects of DDN will lead to the optimal use (e.g., timing, amount, and frequency of DDN administration) clinically to ultimately improve the overall quality of life in patients with spasticity secondary to stroke (herein referred to as 'spasticity').

Available small studies, case reports (14-22), and our preliminary data (87) support that DDN likely produces neural plasticity at both spinal and supraspinal levels. Thus, our central hypothesis is that ***DDN at MTrP induces plasticity in the spinal and supraspinal pathways and produces therapeutic effects.*** While the steady increase in therapeutic use of DDN implies its clinical potential, its optimal use is yet to be established, largely due to the limited mechanistic understanding of its neurophysiological effects. This pilot project is our first step towards understanding the neurophysiological mechanisms of DDN, specifically the spinal mechanisms of DDN-induced plasticity. This project evaluates these mechanisms via two specific aims:

Aim 1. To evaluate the effects of DDN on proprioceptive reflexes in people with spasticity due to stroke.

In people with spasticity the excitability of the H-reflex pathway (an electrical analog of spinal stretch reflex) becomes elevated and reciprocal inhibition of the plantarflexors by the dorsiflexors becomes impaired (25, 26). Thus, to investigate the effects of DDN at the medial gastrocnemius (MG) MTrP on excitatory and inhibitory proprioceptive reflexes, in 20 individuals with spasticity due to stroke we will measure the H-reflex – M-wave (H/M) recruitment curves and reciprocal inhibition in the triceps surae muscles before, immediately after, 90 minutes after, 24 hours after, and 72 hours after DDN. One week prior to DDN, the same measurements will be repeated 5 times, with inter-measurement intervals matching to pre and post DDN measurements. We anticipate that decreases in H-reflex size and reciprocal inhibition will occur between pre and post DDN time points.

Aim 2. To evaluate the effects of DDN on cutaneous reflexes in people with spasticity due to stroke. Modulation of cutaneous reflexes to non-noxious stimulation of the skin become abnormal

post-stroke, reflecting the altered somatosensory processing in this population (33, 34). Thus, in this project, we will examine cutaneous reflex responses to non-noxious stimulation of the distal limb (i.e., at or below the area treated with dry-needling) at the same time points as the proprioceptive reflexes before and after a single DDN session. We anticipate that cutaneous reflex amplitudes will be decreased after DDN.

Additionally, to interpret these reflex changes related to typical clinical measures, we will measure passive and active dorsiflexion range of motion (ROM) and the Modified Ashworth scale, Fugl-Meyer, and 10-m walk test. These measurements will facilitate the development of future DDN clinical trials towards establishing spinal neurophysiological mechanisms of DDN.

The findings from this project would also help clinicians estimate when post DDN motor practice/training therapies should be administered for improving motor function in persons with and without spasticity. The data obtained through this pilot project will significantly strengthen our future NIH R-series applications, through which we plan to test the hypothesis that a single administration of DDN procedures will produce lasting effects on spinal neurophysiology that support temporary relief/alleviation of sensorimotor impairments in people with spasticity due to chronic stroke.

2.0 Background

Sensorimotor disorder after stroke

Spasticity, conventionally seen as increased muscle tone and exaggerated stretch reflexes [12,35-39], is one of the most common and disabling motor control problems after stroke [12,35,36,40]. Together with weakened voluntary muscle contraction [41], it often limits joint movements and results in spastic movement disorders (e.g., circumduction gait). When untreated or treated inappropriately, spasticity may contribute to increased pain and joint contractures, and thereby affect quality of life. Malfunctioning spinal inhibition (including presynaptic inhibition), muscle hypertonus, secondary changes in spinal pathways, and impaired sensory afferent processing and contribution are known contributors to spastic sensorimotor disorders [1,2].

Currently, the most common methods to treat spasticity are pharmacological and physical therapies. Widely applied pharmacotherapy typically disables certain connections (e.g., botulinum toxin) or enhance general inhibition (e.g., baclofen). While its utility has been generally accepted, undesirable side effects may occur [3-13]. Standard methods used in physical therapy, including joint mobilization [42-44] and transcutaneous electrical nerve stimulation [45-47], can also help to reduce spasticity temporally. In recent years, among physical therapists across the US, Europe, and Asia, dry needling has become recognized as a potential alternative tool to treat muscle spasm, spasticity, and pain in people with orthopedic or CNS injuries [16-19,48,49].

Dry needling

As the therapeutic use of dry needling grows, mechanistic understanding of this approach has been building up [21,24,49], although slowly. *Mechanically*, dry needling that targets Myofascial Trigger Points (MTrP) would disrupt dysfunctional motor end plates; that is, needling of MTrPs can stretch the contracted cytoskeletal structures (i.e., shortened sarcomeres) [50] and thereby help to restore the resting level of sarcomere (i.e., muscle fiber) length. Change in the muscle fiber length will then affect the firing of group II muscle spindle afferent, which produces complex effects on the network of spinal inhibitory and excitatory pathways [26,51-54], as well as exciting motoneurons through spinal stretch reflex pathways [55-59].

Physiologically, dry needling stimulates nociceptors (i.e., A- β and A- δ (group II/III) sensory afferents,), which in turn, influences the excitability of multiple spinal pathways (including both excitatory and inhibitory interneurons) [60-64]. This may partly explain pain reduction as a result of

dry needling [19,48,65]. It has been suggested that dry needling also activate serotonergic and noradrenergic systems, which influence the impact of sensory inputs in the spinal dorsal horn [66,67].

Dry needling also affects the local muscle blood flow and oxygen saturation [68,69], which presumably helps to reduce pain-producing substances (e.g., bradykinin, calcitonin gene-related peptide, and Substance P) that are accumulated at/around MTrPs [70,71]. Sustained contractures of taut bands (often felt as palpable contraction knots) cause local ischemia and hypoxia in the MTrPs. Hypoxia, together with myofascial tension, can increase the amount of acetylcholine release at the motor end plate, which can create a self-sustaining vicious cycle of muscle contraction. A drop in pH resulting from low oxygen levels could also excite muscle nociceptors, which sense the peripheral biochemical environment and mediate local blood supply. Sensitized muscle nociceptors have a lower excitation threshold (allodynia) and are more easily respond to muscle movement (mechanical hyperalgesia) [21]. Pain associated with spastic hypertonia can further involve central sensitization. Altered central processing of somatosensory input can be seen in impaired flexor withdrawal reflexes to noxious stimuli and/or impaired cutaneous reflexes to non-noxious stimuli (e.g., [34]). Central sensitization is also the mechanism of referred pain, and involves sensitization and an expansion of receptive fields [21]. For all these reasons, increasing the local blood flow and oxygenation appears to be a key mechanism of action of therapeutic dry needling.

In sum, the current view/presumption is that dry needling can help to restore the functional state of end plate and alleviate hypertonia and hyperalgesia through its immediate mechanical effects on end plate and by increasing the local blood flow and oxygenation. However, to date, its neurophysiological effects on spinal and supraspinal somatosensory processing in people after stroke are not yet understood. To determine the clinical utility of dry needling in treating spasticity and/or related sensorimotor disorders after stroke, it is essential to understand its neurophysiological impact on CNS pathways involved in sensorimotor function. Thus, the goal of this project is to characterize neurophysiological effects of dry needling on spinal and supraspinal somatosensory pathways in people with spasticity due to chronic stroke.

3.0 Intervention to be studied

This project is to examine the neurophysiological mechanisms of trigger point deep dry needling (DDN), a commonly practiced therapeutic method to treat spasticity and pain in individuals with neurological and non-neurological (orthopedic) injuries.

4.0 Inclusion and Exclusion Criteria/ Study Population

Adults (≥ 18 years old) with spastic hyperreflexia due to stroke.

Inclusion criteria are: 1) neurologically stable for >6 months (and >1 yr post stroke); 2) medical clearance to participate; 3) unilateral ankle and/or wrist spasticity, confirmed by Modified Ashworth Scale (MAS) > 1 and the presence of spastic hyperreflexia, 4) ability to ambulate at least 10 m with or without an assistive device (except for parallel bars). For quantifying hyperreflexia, we will measure the H-reflex in the soleus for the lower extremity. We will enroll post-stroke individuals who exhibit abnormally large H-reflexes [25] and abnormally strong reflex activity during the simple motor task [26,72,73] (e.g., walking and reaching and grasping). The H-reflex is completely suppressed in neurologically normal individuals during the swing phase of walking [74], for example, and therefore, testing reflexes during these dynamic movements is useful for evaluating spasticity.

Exclusion criteria are 1) motoneuron injury (i.e. the neurons that give rise to the axons innervating the muscles) with inadequate response to stimulation; 2) a cardiac condition (history of myocardial infarction, congestive heart failure, pacemaker use, coronary artery disease, atrial fibrillation, congenital heart disease, uncontrolled hypertension); 3) a medically unstable condition

(including temporary infections and pregnancy); 4) age <18 years old; 5) cognitive impairment sufficient to interfere with informed consent or successful completion of the protocol; 6) metal allergies; 7) needle phobias; 8) lymphedema over a limb (due to risk of infection/cellulitis); 9) abnormal bleeding tendencies; 10) compromised immune system; 11) vascular disease; 12) uncontrolled diabetes; 13) history of epilepsy (as DDN generates strong somatosensory sensation); 14) anxiety disorders or in distress; 15) botox injection in targeted muscle within 3 months prior to study procedures.

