9.0 Study Design / Methods

This study is a partial cross-over waitlist control design, in which each of the 20 participants post stroke will participate in 7 visits over a two-week period, during which measurements will be taken 10 times. Neurophysiological and functional measurements will be collected five times over 3 visits during the first week (treatment as usual control week), through which each participant will serve as their own "controls" for their second week of measurements. No sham or other treatment procedure will occur during this week. On the second week, all participants will transition to the DDN intervention week where five measurements will be collected over 3 visits (one pre-DDN baseline and four post-DDN measurements: immediately after, 90 minutes, 24 hours, and 72 hours).

Deep Dry Needling (DDN)

DDN procedures used in this project have been widely used in clinical practice to treat spasticity and pain in individuals with neurological and non-neurological (orthopedic) injuries [15,16,18,20,21,48,75].

Each participant receives a single session of DDN, targeting the medial gastrocnemius. In each DDN session, first, localized hypersensitive spots in palpable taut bands of the targeted skeletal muscles (i.e., MTrPs)(75, 76) are identified with pincer palpation. Then, after cleaning the skin area over a MTrPs with alcohol swabs, a disposable stainless steel acupuncture needle is inserted into the skin, penetrating approximately 15 to 20 mm to the depth of the trigger point, until the local twitch response (LTR) is elicited. Once the LTR is confirmed, the needle is moved up and down

(~4-5 mm vertically) with a small piston motions (approximately at 1 Hz for 25 to 30 seconds) with no rotation at the MTrPs (9,10, 38). The same procedure is repeated at other MTrPs in the same local skin region as needed until the LTR is eradicated. After removing the needle, the needled area is rubbed to prevent bleeding and bruising. Each participant will complete 5 repetitions of each of the following: ankle plantarflexion/dorsiflexion passive range of motion (PROM), sub-maximal concentric and eccentric contractions of the plantarflexors as would be typical in a clinical setting.

Electromyography (EMG) and nerve stimulation

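### The MAS half of inclusion criterion 3 can be met at the wrist alone, although only the medial gastrocnemius is needled, so a participant could enter at the ankle MAS floor

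*Combined protocol and SAP*

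**What the plan says.** - **Entry.** Section 4.0, inclusion criterion 3, requires "unilateral ankle and/or wrist spasticity, confirmed by Modified Ashworth Scale (MAS) > 1 and the presence of spastic hyperreflexia". These are two conditions, one on MAS and one on reflexes. The MAS condition may be met at either joint.
- **Reflex screen.** The same section adds: "For quantifying hyperreflexia, we will measure the H-reflex in the soleus for the lower extremity". It enrols people with abnormally large H-reflexes who also show "abnormally strong reflex activity during the simple motor task [26,72,73] (e.g., walking and reaching and grasping"). It gives no numerical cut-off.
- **Treatment.** Section 9.0, under Deep Dry Needling: "Each participant receives a single session of DDN, targeting the medial gastrocnemius".
- **Recording.** Section 9.0, under Electromyography (EMG) and nerve stimulation, places electrodes over the tibialis anterior, both gastrocnemius heads and the soleus of the studied leg. All four stimulation protocols use nerves of the leg.
- **A site-specific rule elsewhere.** Exclusion 15 in Section 4.0 concerns "botox injection in targeted muscle within 3 months prior to study procedures". The eligibility rules are thus tied to the treated muscle in one place and not in criterion 3.
- **Role and scoring of MAS.** Section 1.0 collects MAS, with range of motion and function tests, "to interpret these reflex changes related to typical clinical measures". Section 9.0 scores it from 0 (normal tone) to 4 and does not say at which joint.

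**The concern.** The joint that qualifies a participant on tone need not be the joint on which the needled muscle acts. Someone with wrist MAS above 1 and ankle MAS 0 satisfies the MAS half of criterion 3 as written.

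If the outcome MAS is scored at the ankle, which is the natural reading, that person starts at the bottom of the scale and cannot improve. The sample is fixed at 20, so each such participant is 5% of it and pulls the mean MAS change towards zero. MAS is there to give the reflex changes a clinical meaning. A real reflex change could then seem to have less of a clinical counterpart than it has among people who had ankle tone to lose.

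**Working it through.** The plan states no figure on this point, so there is nothing to reproduce. The check is a comparison of sections followed by one piece of arithmetic.

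**Step 1. Does any rule set a minimum ankle MAS?**

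| Rule | What it secures | Minimum ankle MAS? |
|---|---|---|
| Criterion 3, MAS half (4.0) | MAS above 1 at ankle or wrist | No, the wrist suffices |
| Criterion 3, hyperreflexia half, with the soleus H-reflex screen (4.0) | Abnormal reflexes, measured in the leg | No |
| Criterion 4, walking 10 m (4.0) | Ability to walk | No |
| Taut bands and a local twitch response for needling (9.0) | Trigger points in the needled muscle | No |

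The hyperreflexia half cannot stand in for the MAS half, because criterion 3 lists them as separate requirements. Entry at ankle MAS 0 is therefore permitted.

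**Step 2. How much can this dilute the MAS result?**

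Inputs: n = 20 (Sections 5.0 and 9.0) and a scale floor of 0 (Section 9.0). The number k who start at ankle MAS 0 is not in the documents, so it is assumed over a range. The outcome MAS is taken to be the ankle score.

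Someone at 0 has an improvement of at most 0. If m is the mean improvement among the other 20 − k, then

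mean improvement over all 20 ≤ [(20 − k) × m + k × 0] / 20 = m × (20 − k)/20.

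| k (assumed) | (20 − k)/20 | Upper limit as a share of m |
|---|---|---|
| 0 | 20/20 | 100% |
| 1 | 19/20 | 95% |
| 2 | 18/20 | 90% |
| 4 | 16/20 | 80% |
| 6 | 14/20 | 70% |

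This is a bound on the mean and needs no distributional assumption. Participants starting at ankle MAS 1 also have little room to improve, but they are outside the bound.

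**Step 3. Can this be turned into a loss of power?**

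No. Section 10.0 assigns a Student t-test to changes in sensory and motor function. The plan gives no MAS effect, standard deviation, significance level or power. Any power figure would follow from the inputs chosen for it and not from the plan.

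**The case against.** The strongest reply is that the group at risk is narrow. To do harm, a person must have wrist MAS above 1, an abnormally large soleus H-reflex, abnormal reflex activity in a motor task (the worked example in Section 4.0 is the swing phase of walking) and trigger points in the medial gastrocnemius that can be needled, yet have ankle MAS 0. Nothing in the documents suggests that such people are common. This stands: the share is unknown and may be zero. The filters favour a spastic leg, but none of them closes the gap in the rule.

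A second reply is that both aims concern reflexes and MAS is additional, in a pilot with no MAS hypothesis. This also stands, and it keeps the severity low.

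A reader might infer several stronger points that the documents do not support:

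- **That ankle MAS 0 means no spasticity in the treated leg.** Section 1.0 calls spasticity "defined as a velocity-dependent reaction to passive range of motion, and often is demonstrated concurrently with increased resting muscle tone", which taken alone points that way. But Section 2.0 also describes it as exaggerated stretch reflexes, Aim 1 treats the H-reflex as the electrical analog of the stretch reflex, and Section 4.0 regards reflex testing as useful for evaluating spasticity. Someone at ankle MAS 0 with an abnormally large soleus H-reflex in that leg still shows reflex spasticity.
- **That the H-reflex outcomes are compromised.** If the soleus screen is applied to the studied leg, it largely protects them.
- **That dorsiflexion range of motion also has no room to improve.** Section 2.0 says of spasticity: "Together with weakened voluntary muscle contraction [41], it often limits joint movements". Weakness can limit movement too, so normal ankle tone does not imply full range.
- **That the outcome MAS may be scored at an untreated wrist.** The wording does not rule this out, but Section 1.0 lists MAS alongside dorsiflexion range of motion, and all treatment and recording is in the leg. The unnamed joint is mainly missing detail.

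**Conclusion.** The point holds as a mismatch between criterion 3 and the treatment and recording sections. As written, wrist spasticity alone meets the MAS half of the criterion, and no other rule sets a minimum ankle MAS.

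The consequence is confined to MAS. With k of 20 at ankle MAS 0, mean improvement is capped at (20 − k)/20 of that in the others: 95% for one such participant and 80% for four. This rests on the outcome MAS being scored at the ankle and on an assumed k. If k is zero there is no dilution. No loss of power is claimed.

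Severity is low, because MAS supports the interpretation of the reflex results and is not itself an aim. The wrist wording may be a carry-over from another study, but the documents do not say so, and staff will screen from the text as it stands. The case for acting is that the correction is specific and cheap.

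**What to change.** Reconcile criterion 3 in Section 4.0 with the needling and recording parts of Section 9.0. Both the MAS condition and the hyperreflexia condition should refer to the ankle plantarflexors of the leg that will be needled and recorded. Wrist spasticity may coexist but should not qualify a participant.

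As a consequential clarification, name that same ankle in the Modified Ashworth Scale paragraph of Section 9.0. Removing the upper-limb example from the motor-task description in Section 4.0 would be consistent with this, but it is editorial.

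The cost is a short eligibility amendment and one added phrase in the outcome description. Recruitment becomes slightly narrower, and everyone needs an ankle MAS at screening, which the documents do not say is already taken.

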5.0 Number of Subjects

Twenty adults (≥ 18 years old) with spastic hyperreflexia due to stroke are recruited from the community around the MUSC and a greater Charleston area.

6.0 Setting

The entire procedures will be performed at the College of Health Professions Research Building on the Medical University of South Carolina campus.

7.0 Recruitment Methods

Adults (≥ 18 years old) with spasticity due to stroke are recruited from the community around the MUSC and greater Charleston area. Individuals with stroke will be recruited through word of mouth (i.e. support group meetings, through clinicians, health care providers, and participants). Subjects recruited in this manner will be directed to contact the research team directly. This study will also recruit from the Registry for Stroke Recovery (RESTORE-Pro#00037803, IRB approved 9/6/14) which is a research tool sponsored by the National Institutes of Health (NIH) Center of Biomedical Research Excellence (COBRE) in Stroke Recovery with subjects consented for future contact to support stroke recovery research conducted at MUSC. RESTORE staff will query the registry for potential subjects and provide the Principal Investigator (PI) with the contact information of subjects who meet their criteria. The PI or research staff will contact subjects via phone or email to further screen for potential enrollment.

The research coordinator will be the first study staff to make the contact with a potential participant, obtain the medical records, and pre-screen him/her for eligibility. During this process, the coordinator will mail or email the study consent form to the potential participant. For medical/neurological screening of participants, the pre-screened potential participant will be brought to MUSC for an appointment with the study therapist and investigators, if agreed. The coordinator will obtain the signed consent from the potential participant in person, prior to the in-person medical or EMG screening (i.e., first preliminary session).

The participant will be paid \$45 for the second and fifth sessions, and \$15 for the remaining 5 sessions. S/he will also be provided with transportation reimbursement if needed. The participant will be reimbursed \$0.56 per mile for transportation costs for any distance greater than or equal to 1 mile; or if s/he is using a transportation service (CARTA, etc.), the fee may be reimbursed. The payment (including transportation expense) will be made with cash or ClinCard, even if the participant does not complete the sessions.

